10.3.4. Reporting of SAEs

SAE Reporting to Sponsor via Paper Report Form

- Facsimile/E-Mail transmission of the SAE paper form is the preferred method to transmit this information to Zambon Drug Safety and the Medical Monitor.
- In rare circumstances and in the absence of facsimile equipment, notification by telephone is acceptable with a copy of the SAE data collection tool sent by overnight mail or courier service.
- Initial notification via telephone does not replace the need for the investigator to complete and sign the SAE form within the designated reporting time frames.
- Contacts for SAE reporting can be found on protocol page 3 (Zambon Drug Safety Unit and Medical Monitor contact details.

10.4. Appendix 4: Contraceptive Guidance, Exposure, Sperm Donation and Collection of Pregnancy Information

10.4.1. Contraception

Male subjects who are sexually active with a partner of childbearing potential must use, with their partner, a condom plus an approved method of effective contraception from the time of informed consent until 14 days after their last dose of IMP.

The following methods are acceptable:

Highly Effective Methods of Contraception (to be used by male subjects and their partners)

- Combined (estrogen and progestogen-containing) hormonal contraception associated with inhibition of ovulation:
 - oral
 - intravaginal
 - transdermal
- Progestogen-only hormonal contraception:
 - oral
 - injectable
 - implantable
- Intrauterine hormone-releasing system (IUS)
- Implantable intrauterine device (IUD)
- Surgical sterilisation (for example, vasectomy* or bilateral tubal occlusion/ligation) *For vasectomy, the procedure should have been confirmed as successful and documentation made of this in the subject's notes.

Female subjects who are sexually active and of childbearing potential must use, an approved method of highly effective contraception from the time of informed consent until 30 days after their last dose of IMP.

Highly Effective Methods of Contraception (to be used by female subjects of childbearing potential)

- Combined (estrogen and progestogen-containing) hormonal contraception associated with inhibition of ovulation:
 - oral

- intravaginal
- transdermal
- Progestogen-only hormonal contraception associated with inhibition of ovulation*
 - oral
 - injectable
 - implantable
- IUS
- IUD
- Surgical sterilisation (for example, bilateral tubal occlusion/ligation)
- *The following are not considered highly effective, i.e. not associated with inhibition of ovulation: Micronor, Norgeston, Noriday.

Alternatively, true abstinence is acceptable when it is in line with the subject's preferred and usual lifestyle. If a subject is usually not sexually active but becomes active, they, with their partner, must comply with the contraceptive requirements detailed above.

Female subjects who are not of childbearing potential do not need to use any methods of contraception. A woman is considered of childbearing potential unless post-menopausal or permanently sterile. Permanent sterilisation methods include hysterectomy, bilateral salpingectomy, bilateral oophorectomy and bilateral tubal occlusion/ligation. A post-menopausal state is defined as no menses for 12 months without an alternative medical cause (without hormone replacement therapy [HRT]). If required by the investigator, this may be confirmed by a follicle stimulating hormone (FSH) result of ≥40 IU/L.

10.4.2. Exposure to Partners during the Study

There is a risk of drug exposure through the ejaculate (which also applies to vasectomised males) that might be harmful to the sexual partners (both male and female), including pregnant partners of male subjects. Therefore, a condom should be used by all male subjects throughout the study and for 14 days after their last dose of IMP.

10.4.3. Sperm Donation

Male subjects should not donate sperm for the duration of the study and for at least 14 days after their last dose of IMP.

10.4.4. Collection of Pregnancy Information

Male subjects with partners who become pregnant

- The investigator will attempt to collect pregnancy information on any male subject's female partner who becomes pregnant while the male subject is in this study. This applies only to male subjects who receive IMP.
- After obtaining the necessary signed informed consent from the pregnant female partner directly, the investigator will record pregnancy information on the appropriate form and submit it to the sponsor within 24 hours of learning of the partner's pregnancy. The female partner will also be followed to determine the outcome of the pregnancy. Information on the status of the mother and child will be forwarded to the sponsor. Generally, the follow-up will be no longer than 6 to 8 weeks following the estimated delivery date. Any termination of the pregnancy will be reported regardless of fetal status (presence or absence of anomalies) or indication for the procedure.

Female subjects who become pregnant

- The investigator will collect pregnancy information on any female subject who becomes pregnant while participating in this study. The initial information will be recorded on the appropriate form and submitted to the sponsor within 24 hours of learning of a subject's pregnancy.
- The subject will be followed to determine the outcome of the pregnancy after signature of a specific Informed Consent for Pregnancy Follow up. The investigator will collect follow-up information on the subject and the neonate and the information will be forwarded to the sponsor. Generally, follow-up will not be required for longer than 6 to 8 weeks beyond the estimated delivery date. Any termination of pregnancy will be reported, regardless of fetal status (presence or absence of anomalies) or indication for the procedure.
- While pregnancy itself is not considered to be an AE or SAE, any pregnancy complication or elective termination of a pregnancy for medical reasons will be reported as an AE or SAE.
- A spontaneous abortion (occurring at <22 weeks gestational age) or still birth (occurring at >22 weeks gestational age) is always considered to be an SAE and will be reported as such.
- Any post-study pregnancy-related SAE considered related to IMP by the investigator will be reported to the sponsor as described in Appendix 3. While the investigator is not obligated to actively seek this information in former study subjects, he or she may learn of an SAE through spontaneous reporting.
- Any female subject who becomes pregnant while participating in the study will be withdrawn from IMP. A male subject will be withdrawn from IMP in the event that his female partner becomes pregnant.

Clinical Pharmacology Study in Healthy and Asthmatic Subjects Clinical Study Protocol – Study Z7240J01 Version 1.2; 04 June 2020 – Amendment 02

CONFIDENTIAL

All pregnancies during the study will be reported to Zambon Drug Safety and the Medical Monitor (contact details on protocol page 3).

10.5. Appendix 5: Abbreviations

ABPA Allergic Bronchopulmonary Aspergillosis

ADM Admission

AE Adverse Event

AESIs Adverse Event of Special Interest

ALT Alanine Aminotransferase

ANOVA Analysis of Variance

AST Aspartate Aminotransferase

AUC Area Under the Serum Concentration-Time Curve

AUC_{0-t} Area under the Serum Concentration-Time Curve from Time Zero to

the Last Measurable Concentration

AUC_{0-inf} Area Under the Serum Concentration-Time Curve from Time Zero to

Infinity

AUC_{0-tau} Area Under the Serum Concentration-Time Curve from Time Zero to

the End of the Dosing Period

AUCtau Area Under the Serum Concentration-Time Curve to the End of the

Dosing Interval
BID Twice Daily

BMI Body Mass Index

CCF Congestive Cardiac Failure

CE-marked Conformité Européene (European Conformity)

CF Cystic Fibrosis

CFR Code of Federal Regulations

CI Confidence Interval

CIOMS Council for International Organizations of Medical Sciences

CK Creatine Kinase

CL/F Apparent Total Clearance of the Drug from the Serum

C_{max} Maximum Serum Concentration

C_{max,ss} Maximum Steady-State Serum Concentration During a Dosing

Interval

C_{min} Minimum Serum Concentration COVID-19 Corona Virus Disease 2019

CRF Case Report Form

CRO Contract Research Organisation

Css,av Average Steady-State Serum Drug Concentration During Multiple-

Dose Administration

Ctrough Trough Serum Concentration

CYP2C19 Cytochrome p450 2C19
CYP3A4 Cytochrome p450 3A4
DPI Dry Powder Inhaler

DMC Data Monitoring Committee

EC Ethics Committee
ECG Electrocardiogram

eCRF Electronic Case Report Form EDV Early Discontinuation Visit

EU European Union

EudraCT European Union Drug Regulating Authorities Clinical Trials

FEV₁ Forced Expiratory Volume in 1 Sec

FIH First in Human

FSH Follicle Stimulating Hormone

FVC Forced Vital Capacity

g Grams

GCP Good Clinical practice

GDPR General Data Protection Regulation

GGT Gamma Glutamyl Transferase
GLI Global Lung Function Initiative
GMP Good Manufacturing Practice

GMR Geometric Mean Ratio
GP General Practitioner

HB Hepatitis B

HBsAg Hepatitis B Surface Antigen hCG Human Chorionic Gonadotropin

HCV Hepatitis C Virus

HCV Ab Hepatitis C Virus Antibody

HIV Human Immunodeficiency Virus

HIPAA Health Insurance Portability and Accountability Act

HPMC Hydroxypropyl Methylcellulose HRT Hormone Replacement Therapy

IB Investigator's Brochure ICF Informed Consent Form

ICH International Council for Harmonisation

ICS Inhaled Corticosteroid

IEC Independent Ethics Committees

Ig Immunoglobulin
IgE Immunoglobulin E
IgG Immunoglobulin G

IL-4 Interleukin-4 IL-5 Interleukin-5

IMP Investigational Medicinal Product
HPMC Hydroxypropyl Methylcellulose

ISF Investigator Site File
IUD Intrauterine Device

IUS Intrauterine Hormone-Releasing System

Kel Apparent First-Order Terminal Elimination Rate Constant

LABA Long-Acting Beta-Agonist

LAMA Long-Acting Muscarinic Antagonists

LDH Lactate Dehydrogenase Loge Natural Logarithmic

MAD Multiple Ascending Dose MCH Mean Cell Haemoglobin

MCHC Mean Cell Haemoglobin Concentration

MCV Mean Cell Volume

Mg Milligrams

MHRA Medicines and Healthcare Products Regulatory Agency

MIC Minimum Inhibitory Concentration

mL Millilitres msec Millisecond

NOAEL No-Observed-Adverse-Effect Level

RT-PCR Reverse Transcription Polymerase Chain Reaction

PD Pharmacodynamic

PEFR Peak Expiratory Flow Rate
Ph. Eur European Pharmacopoeia

PI Principal Investigator

PIS Participant Information Sheet

PK Pharmacokinetic(s)

PKNCA Pharmacokinetic Complete Noncompartmental analysis

PVC Packed Cell Volume
QA Quality Assurance

QD Once Daily

QP Qualified Person
Q.s Quantum Satis

QTcF QT Interval Corrected for Heart Rate Using Fridericia's Formula

R&D Research and Development

RBC Red Blood Cell
RNA Ribonucleic Acid

SABA Short-Acting Beta-Agonists
SAC Safety Advisory Committee
SAD Single Ascending Dose
SAE Serious Adverse Event
SAF Safety Analysis Set

SAFS Severe Asthma Associated with Fungal Sensitization

SAMA Short-Acting Muscarinic Antagonist

SAP Statistical Analysis Plan

SARS-CoV-2 Severe Acute Respiratory Syndrome Coronavirus 2

SOA Schedule of Activities SOC System Organ Class

SOP Standard Operating Procedure

SPF Sun Protection Factor

Spp Several Species SQN Syne Qua Non

SUSAR Suspected Unexpected Serious Adverse Reaction

t_{1/2} Elimination Half Life
TBD To be Determined

TDL The Doctor's Laboratory

Th2 T-helper Type 2

t_{max} Time to Reach Maximum Serum Concentration

t_{max,ss} Time to Reach Maximum Serum Concentration Following Drug

Administration at a steady state

TP Treatment Period UK United Kingdom

ULN Upper Limit of Normal

Vz/F Volume of Distribution During Terminal Phase After Non-Intravenous

Administration

WBC White Blood Cell

µg Micrograms

% fluctuation Percentage Fluctuation Over the Dosing Interval

% swing Percentage Swing Over the Dosing Interval

10.6. Appendix 6: Protocol Amendment History

The Protocol Amendment Summary of Changes Table for the current amendment is located directly before the Table of Contents (TOC).

Amendment 01, Protocol Version 1.1: dated 14 February 2020:

This amendment is considered to be non-substantial based on the criteria set forth in Article 10(a) of Directive 2001/20/EC of the European Parliament and the Council of the European Union because it neither significantly impacts the safety or physical/mental integrity of participants nor the scientific value of the study.

Overall Rationale for the Amendment:

The overall rationale for the changes implemented in this protocol amendment is to correct Typographical errors throughout.

Section # and Name	Description of Change	Brief Rationale
Appendix 10.4	Typographical errors corrected	'Highly' effective methods of contraception for males are to be followed to match inclusion criteria 4 (Part 1), inclusion criteria 6 (Part 2 & Part 3).
		Contraception option for 'Male condom with either female cap or diaphragm (double barrier) plus spermicide' removed from list for male subjects since this is not listed as a CTFG 'highly effective' method of contraception.
		IUS listed separately as a highly effective form of contraception for both male and female subjects, originally listed under progesterone only contraception in error

Section # and Name	Description of Change	Brief Rationale
Section 8.14.1, Section 9.3, Section 9.4.4, Section 10.5	Typographical errors corrected	Corrected to reflect the serum samples that are required for the serum PK analysis.

Protocol Version 1.0: dated 13 December 2019.

Original protocol.

11. References

- 1. Ashok Shah et.al (2016) Allergic Bronchopulmonary Aspergillosis: A Perplexing Clinical Entity; Allergy Asthma Immunol Res. 2016 Jul; 8(4): 282–297. Published online 2016 Mar 17. https://www.ncbi.nlm.nih.gov/pmc/articles/PMC4853505/

# **Modification History**

Version	Change History	Reason	Date 12AUG2020
1.0	First Version	N/A	
2.0	
 
Update to protocol deviations listing to only important PDs
 
Removed exposure table from analysis
 
Updated AESI to tabulate if necessary
 
Added Sputum plug and processed sputum to analysis
 
	
 
To bring in line with SQN current processes
 
Following client review of dry run TFL
 
	280CT2020

#### LIST OF ABBREVIATIONS

AE	Adverse Event
AESI	Adverse Event of Special Interest
ALT	Alanine Aminotransferase
ANOVA	Analysis of Variance
AST	Aspartate Aminotransferase
AUC 0-t	Area Under the Concentration time curve over the Dosing Interval
AUC 0-inf	Area Under the Concentration time curve from time Zero to Infinity
AUC tau	Area Under the Concentration curve from time Zero to the End of the dosing period
BLQ	Below limit quantification
BMI	Body Mass Index
CI	Confidence Interval
CL/F	Apparent total clearance of the drug from the serum
C min	Minimum Observed Concentration
C max	Maximum Observed Concentration
C max,ss	Maximum Observed Concentration following drug administration at a steady state
CS	Clinically Significant
CV	Coefficient of Variation
ECG	Electrocardiogram
eCRF	Electronic Case Report Form
FEV 1	Forced Expiratory Volume in 1 second
FVC	Forced Vital Capacity
GMR	Geometric Mean Ratio
IMP	Investigational Medicinal Product
K el	Apparent First-Order Terminal Elimination Rate Constant
Log e	Natural Logarithm
MAD	Multiple Ascending Dose
MedDRA	Medical Dictionary for Regulatory Activities
NC	Not calculated
NCS	Not Clinically Significant
NR	No Result
PEFR	Peak Expiratory Flow Rate
PK	Pharmacokinetic
PT	Preferred Term
Date: 280CT2020	Page 4 of 20

R ac	Accumulation Ratio				
SAC	Safety Advisory Committee				
SAD	Single Ascending Dose				
SAF	Safety Analysis Set				
SAP	Statistical Analysis Plan				
SD	Standard Deviation				
SOC	System Organ Class				
t 1/2	Terminal Elimination Half-Life				
TEAE	Treatment Emergent Adverse Event				
t max	Time of the Maximum Observed Concentration				
t max,ss	Time of the Maximum Observed Concentration following drug administration at a steady state				
ULN	Upper Normal Limit				
Vz/F	Volume of Distribution During Terminal Phase After Non-Intravenous Administration				
WHO Drug	World Health Organization Drug Dictionary				
% fluctuation	Percentage Fluctuation Over the Dosing Interval				
% swing	Percentage Swing Over the Dosing Interval				

## 1 INTRODUCTION

This document details the statistical analysis that will be performed for the Zambon study: A Phase 1, Three-Part, Open-Label Study to Assess the Safety, Tolerability and Pharmacokinetics of Single Doses of Inhaled Voriconazole (ZP-059) in Healthy Subjects (Part 1), Multiple Doses of ZP-059 in Mild Stable Asthma Subjects (Part 2) and in a Two-Period Crossover Study of Single Doses of ZP-059 and Single Doses of Oral Voriconazole in Mild to Moderate Stable Asthma Subjects (Part 3).

The proposed analysis is based on the contents of the Final Version of the protocol (dated 13th December 2019), amendment 1 (dated 14th February 2020) and amendment 2 (dated 04 June 2020). In the event of future amendments to the protocol, this statistical analysis plan (SAP) may be modified to account for changes relevant to the statistical analysis.

The table, listing and figure shells are supplied in a separate document.

## 2 CHANGES FROM THE PROTOCOL PLANNED ANALYSIS

For the PK analysis, linearity ratios will not be reported due to the likelihood that  $AUC_{0-}$  inf cannot be obtained.

## 3 STUDY OBJECTIVES AND DESIGN

## 3.1 Study Objectives

#### 3.1.1 Primary Objectives

The primary objectives of the study are:

- Part 1: To determine the safety and tolerability of single inhaled doses of ZP-059 in healthy subjects.
- Part 2: To determine the safety and tolerability of multiple inhaled doses of ZP-059 in subjects with mild stable asthma.
- Part 3: To determine the safety and tolerability of single inhaled doses of ZP-059 and Oral Voriconazole in subjects with mild to moderate stable asthma.

#### 3.1.2 Pharmacokinetic (PK) Objectives

The PK objectives of the study are:

- Part 1: To characterise systemic PK of voriconazole and N-oxide voriconazole after single doses of ZP-059 in healthy subjects.
- Part 2: To characterise systemic PK of voriconazole and N-oxide voriconazole after multiple doses of ZP-059 in subjects with mild, stable asthma.
- Part 3: To characterise systemic PK of voriconazole and N-oxide voriconazole after single doses of ZP-059 and single doses of oral voriconazole in subjects with mild to moderate stable asthma.

#### 3.1.3 Exploratory Objectives

The exploratory objectives of the study are:

- Part 1: None
- Part 2: To characterise voriconazole and N-oxide voriconazole concentrations in induced sputum after multiple doses of ZP-059 (i.e. on Day 7; both pre-dose and post-dose) in subjects with mild, stable asthma.
- Part 3: To characterise voriconazole concentrations and N-oxide voriconazole in induced sputum after single inhaled doses of ZP-059 and after single doses of oral voriconazole in subjects with mild to moderate stable asthma.

## 3.2 Study Endpoints

#### 3.2.1 **Primary Endpoints**

The primary endpoint for each Part (Part 1, 2, & 3) of the study is:

 Safety and tolerability, as assessed by monitoring of adverse events (AEs), physical examinations, changes in vital signs, clinical laboratory parameters, electrocardiogram (ECG), pulse oximetry and spirometry assessments (forced expiratory volume in 1 second (FEV1), forced vital capacity (FVC), peak expiratory flow rate (PEFR) and FEV1/FVC).

#### 3.2.2 Pharmacokinetic (PK) Endpoints

The PK endpoints to analyse both voriconazole and N-oxide voriconazole for each part (Part 1, 2, & 3) of the study are:

- Parts 1, 2 and 3 (in Part 3, Day 1 of Treatment Period 1 and Day 1 of Treatment Period 2):
  - AUC0-t; where 't' is the last timepoint at which concentrations were quantifiable, nominally 12 h, 24 h & 96 h for Parts 1, 2 and 3 respectively. Note that the last timepoint, t, may differ depending on the actual data and dose regimen.
  - $\circ$  AUC0-inf. Note that if dosing is twice daily robust estimation of AUC0-inf on Day 1 part 2 may prove challenging.
  - AUCtau; Part 2, Day 1 only
  - $\circ$   $C_{max}$
  - o tmax
  - Kel; except Part 2 (day 1)
  - $\circ$  t1/2; except Part 2 (day 1)
- Part 2 (Day 10):
  - $\circ$  AUCtau,
  - o Cmax,ss
  - tmax,ss
  - $\circ \quad C_{ss,av}$
  - %fluctuation and swing (as appropriate and when applicable)
  - Accumulation (Rac) based on the ratio of Day 10 AUCtau to Day 1 AUCtau
  - $\circ~$  Pre-dose concentrations measured on Days 3 to 10 will be designated as  $C_{\text{min}}$  values
- For voriconazole only CL/F and Vz/F will be estimated from Part 1, Part 2 (Day 10) and Part 3 serum concentration data

These will be assessed using the serum concentration for voriconazole and N-oxide voriconazole.

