9.4.4. PK Analysis

The PK endpoints for statistical analysis, which will be assessed using serum concentrations for both voriconazole and N-oxide voriconazole are:

Maximum observed serum concentration (Cmax)

- AUC Area under the serum concentration curve from zero to time of the last quantifiable concentration (AUC0-t), where t is 12 hours for Part 1, 24 hours for Part 2 and 96 hours for Part 3.
- Area under the serum concentration curve from zero extrapolated to infinity (AUC0-inf).

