## 7.12 Pharmacokinetics

#### 7.12.1 Serum concentrations

Serum concentrations of both voriconazole and N-oxide voriconazole will be summarised over time and listed for those in the PK Concentration set. Mean, SD, minimum, maximum and median will be presented.

Similar analyses will be completed for the PK parameters listed in section 3.2.2 for those subjects in the PK Parameters set. Additionally, the geometric mean, CV% and geometric SD will also be presented.

Mean (±SD) serum concentration profiles will be plotted on the original scale and on the log scale. Samples below limit of quantification (BLQ) prior to the first quantifiable concentration will be set to zero. Samples with concentrations BLQ after the first quantifiable concentration will be set to 'missing' and omitted from the analysis. Other PK parameters will be calculated according to standard equations.

If a value is considered to be anomalous due to being inconsistent with the expected PK profile, it may be appropriate to exclude this point from the PK analysis. However, the exclusion of data must have strong justification and will be documented in the raw data and in the clinical study report. The following conditions for PK parameter inclusion may also be applied:

- AUC0-inf, kel, t1/2, CL/F (exception Part 2, Day 10) and Vz/F to be excluded if the regression does not include at least 3 different time points in the terminal phase (after Cmax, but excluding the concentration at tmax)
- AUC0-inf, CL/F (exception Part 2, Day 10) and Vz/F, t1/2, kel to be excluded if the coefficient of determination, Adjusted R^2 in the regression, is less than 0.8
- AUC0-inf, CL/F and Vz/F is excluded if the %extrapolated area is greater than 20% (exception CL/F and Vz/F in Part 2, Day 10)

Metabolite parent ratios will be estimated for  $C_{max}$  and AUC across all parts of the study.

The following rules will be applied if there are BLQ or missing values (e.g. no result (NR)) in serum concentration data series to be summarised:

- If an embedded BLQ value was set to missing for PK analysis, this value will be excluded from the summary statistics. Other BLQ values will be set to 0.
- NR results will be set to missing.

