#### 7.12.3 Dose proportionality

Dose proportionality of ZP-059 will be assessed by fitting a power model as follows:

$$log_{10}(y) = \alpha + \beta \ log_{10}(dose)$$

Where  $\alpha$  represents the random subject effects for intercept and dose. A value of 1 for  $\beta$  indicates perfect dose proportionality. Therefore, the estimate of  $\beta$  together with the corresponding 90% confidence interval (CI) will be used to quantify dose proportionality. The increase in concentration over the dose range will be estimated by the ratio of the expected concentration with the highest dose to that of the lowest dose. This will be derived by back-transforming the difference on the log10 scale between the two doses and will be accompanied by its associated 90% confidence interval. If the exposure is dose proportional there should be a fold increase equal to the ratio of highest: lowest dose across the dose range.

If it isn't possible to fit random subject slopes a common fixed effect slope will be fitted.

Dose proportionality will be assessed for each of the following PK endpoints for voriconazole and n-oxide voriconazole separately:

- Cmax
- AUC0-t, where t is 12 hours for Part 1, 24 hours for Part 2 and 96 hours for Part 3.
- AUC0-inf

These will be performed separately for Part 1 and Part 2 at Day 1 and Day 10. This analysis will be performed if 3 or more dose levels are used for the Part.

Dose proportionality will also be assessed using an analysis of variance (ANOVA) method. A mixed effects model will be fitted with fixed effects for dose and random effects for subject. The difference between the dose levels will be presented along with a 90% confidence interval and p-value.

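### AUC0-t has conflicting definitions and no rule for late samples below the assay limit, so the integration window can shorten as the dose falls and bias the dose-proportionality slope and the inhaled/oral ratio

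*SAP*

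**What the plan says.** The same symbol carries three meanings.

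- **To the last quantifiable sample.** In SAP 3.2.2, t "is the last timepoint at which concentrations were quantifiable, nominally 12 h, 24 h & 96 h for Parts 1, 2 and 3 respectively", followed by "Note that the last timepoint, t, may differ depending on the actual data and dose regimen". The protocol's abbreviation list (10.5) also ends the area at the last measurable concentration.
- **Over a fixed window.** SAP 7.12.3 lists AUC0-t for the power model "where t is 12 hours for Part 1, 24 hours for Part 2 and 96 hours for Part 3". SAP 7.12.4 refers back to that list for the Part 3 inhaled/oral comparison. Protocol 3.2.2 likewise writes AUC0-12, AUC0-24 and AUC0-96.
- **Over the dosing interval.** The SAP abbreviation list gives "Area Under the Concentration time curve over the Dosing Interval".

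Protocol 9.4.4 puts the first two into one definition: "Area under the serum concentration curve from zero to time of the last quantifiable concentration (AUC0-t), where t is 12 hours for Part 1". No passage says which meaning prevails.

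On late samples, SAP 7.12.1 says: "Samples with concentrations BLQ after the first quantifiable concentration will be set to 'missing' and omitted from the analysis". It does not say how an area to 12, 24 or 96 hours is obtained when the last samples have been removed in this way.

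**The concern.** Two programmers could each follow the SAP and report different AUCs. The larger difficulty is that choosing the fixed-window wording does not settle the matter. With late BLQ samples omitted and nothing to replace them, a nominal AUC0-12 still ends at tlast.

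If profiles decline in parallel, a lower dose crosses the assay limit earlier. The area for 5 mg may then cover 4 hours while that for 40 mg covers 12. The missing piece is read as lower exposure at the lower dose, so exactly proportional kinetics give a slope above 1. The same mechanism lowers the ratio of an inhaled dose of at most 40 mg to 200 mg oral.

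The sampling times make Parts 1 and 2 sensitive. PK samples are at 1.5, 2, 3, 4 and 12 hours (plus 24 hours in Part 2), so one BLQ result at 12 hours cuts the window from 12 hours to 4. At stake are two reported estimates with 90% confidence intervals: the slope in SAP 7.12.3 and the geometric mean ratio in SAP 7.12.4.

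**Working it through.** The plan states no figure to reproduce: the study is not powered and gives no expected slope or ratio. The check asks what AUC to tlast returns when the truth is known.

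**Inputs from the documents.** Lowest Part 1 dose 5 mg, ceiling 40 mg (protocol 4.1.1); PK sampling times (protocol 1.2.1 to 1.2.3); 200 mg oral in Part 3 (protocol 4.1.3); BLQ rule (SAP 7.12.1); benchmark slope of 1 (SAP 7.12.3).

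**Assumptions, because the documents are silent.** Doses 5/10/20/40 mg (cohorts 2 to 4 are to be determined); half-life T; lower limit of quantification (LLOQ); linear kinetics.

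**Part 1, by hand.** Let r = AUC0-4/AUC0-12. For four doses equally spaced on the log scale, the least-squares weights on log2(AUC) are -0.3, -0.1, 0.1 and 0.3. With a true slope of 1:

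- only 5 mg cut at 4 h: slope = 1 + 0.3 × log2(1/r)
- 5 and 10 mg cut at 4 h: slope = 1 + 0.4 × log2(1/r)
- no dose cut, or all cut at the same time: slope = 1

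For mono-exponential decline, r = (1 - 2^(-4/T)) / (1 - 2^(-12/T)).

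- T = 4 h: r = 0.500/0.875 = 0.571 and log2(1/r) = 0.807. Slope 1.24 (one dose cut) or 1.32 (two).
- T = 6 h: r = 0.370/0.750 = 0.493 and log2(1/r) = 1.019. Slope 1.31 or 1.41.

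**Part 1, with absorption.** One-compartment profile, absorption rate 2/h, linear-up/log-down trapezoids on the actual sampling times:

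| T (h) | LLOQ, % of 5 mg Cmax | tlast at 5/10/20/40 mg (h) | slope |
|---|---|---|---|
| 2 | 5 | 4/12/12/12 | 1.17 |
| 3 | 5 | 12/12/12/12 | 1.00 |
| 3 | 10 | 4/12/12/12 | 1.25 |
| 3 | 20 | 4/4/12/12 | 1.34 |
| 4 | 20 | 4/12/12/12 | 1.31 |
| 4 | 40 | 4/4/12/12 | 1.41 |
| 6 | 30 | 12/12/12/12 | 1.00 |
| 6 | 40 | 4/12/12/12 | 1.37 |

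A common window (AUC0-12, or AUC0-4 where all samples to 4 h are quantifiable) gives 1.00 in every row.

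**Part 1, with variability.** With 6 subjects per dose, 50% CV and 1500 runs, at T of 3 or 6 h and LLOQ of 5 to 30% of the 5 mg Cmax, the mean slope to tlast is 1.00 to 1.24. Coverage of 1 by the 90% interval falls to 0.64 in the worst case (T = 3 h, LLOQ 30%). With a fixed window, coverage is 0.89 to 0.91.

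**Part 2, Day 1.** The same deterministic check on the 0 to 24 h times gives slopes of 1.00 to 1.48.

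**Part 3.** The table shows (inhaled/oral ratio to tlast) divided by (true 0 to 96 h ratio), for T of 3 to 12 h and LLOQ of 0.05 to 2% of the oral Cmax:

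| Inhaled dose | relative bias |
|---|---|
| 40 mg | 0.79 to 1.00 |
| 20 mg | 0.71 to 1.00 |
| 10 mg | 0.56 to 1.00 |
| 5 mg | 0.23 to 0.98 |

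At 40 mg with LLOQ of 0.05 or 0.1% of the oral Cmax, the figure is 0.94 to 1.00. Dividing by the true ratio cancels the dose difference, so this does not depend on dose normalisation, which SAP 7.12.4 does not specify. Equal bioavailability was assumed only to isolate the window effect.

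**Can AUC0-inf stand in?** SAP 7.12.1 excludes it when more than 20% is extrapolated. For mono-exponential decline the extrapolated share is 2^(-tlast/T), which passes 20% once T exceeds tlast × ln2/ln5: 5.2 h for tlast = 12 h, and 1.7 h for tlast = 4 h. SAP section 2 itself expects that AUC0-inf may not be obtainable.

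**The case against.** The best reply is that the analysis sections already point to a fixed window: SAP 7.12.3 names the hours, 7.12.4 uses that list, and the protocol writes AUC0-12, AUC0-24 and AUC0-96. On this view the variable t belongs to a descriptive endpoint list and the dosing-interval wording is a slip. That is a fair reading. A reader might infer that the plan directs the formal models to use each subject's own tlast, and the documents do not say so. What stands is the missing completion rule: with late BLQ samples omitted, the fixed-window reading reaches the same place.

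The consequence is also limited. Safety is the primary objective, dose escalation rests on safety data, nothing is powered, and Cmax does not depend on the window. All of that holds. It lowers the stakes, but estimates with confidence intervals are still reported. The protocol's like-for-like re-derivation aligns nominal time points between Part 3 and Parts 1 and 2. It does not align tlast across doses or between inhaled and oral.

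Two stronger numerical readings are tempting and fail.

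- With parallel decline, the tlast gap over 5 to 40 mg would be log2(8) = 3 half-lives (18 h at T = 6 h) whatever the LLOQ. Part 1 sampling ends at 12 h, so that gap cannot appear there, and the bias still depends on the LLOQ.
- Slopes of 1.5 or more can be produced by setting the 40 mg concentration at 12 h to twice the LLOQ. With mono-exponential decline this gives 1.32 at T = 4 h and 1.62 at T = 5 h. At T = 6 h the 5 mg dose has no quantifiable sample at all. Figures that unstable should not be relied on.

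**Conclusion.** The conflict is in the current text of both documents, and the BLQ rule turns it into a possible bias of known direction: slope upward, inhaled/oral ratio downward. The size cannot be fixed from the documents. It is nil if all samples to the window end are quantifiable, or if every dose compared has the same tlast. In Part 1, assuming 5/10/20/40 mg and a true slope of 1, it is about 1.2 to 1.4 when one or more of the lower doses are BLQ at 12 h but remain quantifiable to 4 h. In Part 3 it is 0 to 6% at 40 mg with a low LLOQ and larger at lower inhaled doses. These figures rest on linear kinetics and on the half-life and LLOQ ranges shown. They show what the rule permits and do not predict what this trial will find. The point should be settled in the SAP, but it does not touch the safety conclusions.

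**What to change.** In SAP 3.2.2, 7.12.3 and 7.12.4, define the analysed AUC as one fixed window common to everything compared: AUC0-12 in Part 1, AUCtau in Part 2, and one stated window for both treatments in Part 3. If once-daily and twice-daily cohorts enter the same Part 2 model, tau is not common and a single length must be named.

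If tlast falls before the window end:

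- Complete the area with the subject's own terminal slope only when the SAP 7.12.1 regression criteria are met.
- Otherwise set that subject's fixed-window AUC to not calculable and flag it. Do not count the remainder as zero, because that simply returns AUC to tlast.
- Where such subjects occur, also analyse the longest window quantifiable at all doses or treatments compared, for example AUC0-4 in Part 1.

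Tabulate tlast by dose and treatment. Report AUC to tlast under its own symbol as descriptive, and correct the abbreviation list.

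The cost is SAP wording and a derivation rule, with no new data. There are three downsides. The completion can be substantial: under mono-exponential decline, 4 to 12 h is 1 - r = 43% of AUC0-12 at T = 4 h and 51% at T = 6 h. It will often be unavailable: three points after tmax with tlast at 4 h require tmax at the 1.5 h sample. Subjects set to not calculable will tend to be those with low exposure, so the fixed-window result must be read beside the shorter common window, which keeps them but discards some late data.
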